10.4.2 Statistical hypothesis, model, and method of analysis

The primary efficacy analysis will be the comparison of PFS-1 between the two treatment groups using a log-rank test at one-sided 2.5% level of significance.

Assuming proportional hazards model for PFS, the following statistical hypotheses will be tested to address the primary efficacy objective:

$$H_{01}: \theta_1 \geq 0 \text{ vs. } H_{a1}: \theta_1 < 0$$

where θ_1 is the log-hazard ratio (test treatment arm vs. control treatment arm) of PFS.

[figure not shown]
The primary efficacy endpoint PFS-1 will be analyzed at the interim look and final look of a group sequential design based on the FAS population according to the treatment group patients were randomized. PFS will be estimated using the Kaplan-Meier method. The median PFS along with 95% confidence intervals (when applicable) will be presented by treatment group.

A Cox regression model will be used to estimate the hazard ratio of PFS, along with 95% confidence interval.

10.4.3 Handling of missing values/censoring/discontinuations

PFS will be censored if no PFS event is observed before the cut-off date or the date when a new anti-neoplastic therapy or another investigational treatment is started, whichever occurs earlier. The censoring date will be the date of last adequate assessment before either of these two dates. If a PFS event is observed after at least two consecutive missing assessments (corresponding to a minimum of 24 weeks), then PFS will be censored at the last adequate assessment prior to the first missing value. If a PFS event is observed after a single missing assessment, the actual date of event will be used and PFS will not be censored.

Since the definition of progression in this study is multimodal the term assessment corresponds to either spleen palpation, laboratory assessment of hematology parameters (hemoglobin, WBC, peripheral blast count) or MF-7 questionnaire. Adequate assessment requires non-missing assessment for all components of PFS.

For each assessment, the assessment date is calculated as the latest of all measurement dates (e.g. laboratory, MRI) if there is no progression. Otherwise, in case of progression the assessment date is calculated as the earliest date of all measurement dates at that evaluation number.

If a patient permanently discontinues study treatment for reason other than disease progression and progression event occurs between permanent discontinuation and start of new anti-neoplastic treatment then the PFS time will be censored at last adequate assessment date prior to discontinuation of study treatment.

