7.1.4 Treatment Period

Treatment Period 1

Blinded study treatment will be initiated on Day 1 after randomization and treatment assignment by IRT system. Day 1 is defined as the first day of study treatment. After day 1, visits will occur at the following frequency as specified in Table 7-1.

- Every 4 weeks until week 24 (+/- 3 days)
- Every 8 weeks until week 48 (+/- 7 days)
Note: Week 36 visit is required only for MRI/CT of the spleen.
- Every 12 weeks until the end of treatment (+/- 7 days)

Blinded treatment will be administered until disease progression or patient discontinuation.

Treatment Period 2

[figure not shown]
Patients progressing due to splenomegaly or symptom (MF-7 score) in Treatment Period 1 will enter the ruxolitinib Treatment Period 2. All patients are required to have an End of Treatment Period 1 assessment prior to entering Treatment Period 2. All End of Treatment Period 1 assessments should be performed within 2 weeks prior to the first dose of ruxolitinib in Treatment Period 2. The End of treatment bone marrow biopsy and MRI/CT assessments should follow the schedule as per Section 7.2.1.1. The schedule of assessments for patients entering Treatment Period 2 will continue from when the patient discontinued in Treatment Period 1 (Table 7-1 [B]).

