7.2 Assessment types

7.2.1 Efficacy assessments

7.2.1.1 Assessments for primary efficacy endpoint (progression free survival – PFS-1)

The criteria for disease progression (PFS-1) will be assessed for determination of the primary endpoint of progression free survival in accordance with [Section 10.4.1](#). For patients meeting the progressive disease criteria the Investigator must review according to the guidance below, and confirm the relevant criterion. The data should be entered in the appropriate CRF and IRT notified.

Guidance for progressive disease criterion assessment:

- Earliest confirmed single disease progression criterion should be entered.
- If more than one criterion are confirmed on the same date, time or visit (+ 14 days from the date of first confirmed criterion); progressive disease should be assessed using the single criterion based on the hierarchy below:
 1. Death
 2. Leukemic transformation
 3. Splenomegaly
 4. Symptom (MF-7 score)
 5. Hematologic criteria. Note: In the case of more than one hematologic criteria, the investigator should assess the key contributing criterion to declare disease progression

The following assessments will be utilized to assess and confirm disease progression.

1. Spleen volume determination by MRI/CT:

Evaluation of progressive splenomegaly will be performed by regular assessments of spleen volumes via Magnetic Resonance Imaging (MRI) or Computed Tomography (CT) where MRI is contraindicated to ensure an objective and unbiased assessment. MRI (or CT) of the spleen will be performed at screening (within 7 days prior to randomization), every 12 weeks and at the end of treatment ([Table 7-1](#)). An end of treatment MRI (or CT) assessment is only required for patients who discontinue treatment due to disease progression if a MRI (or CT) scan was not performed within 6 weeks of study treatment discontinuation. Patients who enter the post treatment follow up phase after study treatment discontinuation for reasons other than disease progression should have their assessments performed as per the visit schedule at the time of discontinuation.

A designated central imaging laboratory will be used to collect all imaging data; perform quality check and provide read-out for the study. The scans from an individual patient will be read by a central reader upon transfer from the site radiologist. Results from the central evaluations will be used for primary analyses.

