10.4.1 Variable

The primary endpoint is **progression free survival (PFS-1) in Treatment Period 1**. It is defined as the time from date of randomization until earliest time for one of the following events:

- Progressive splenomegaly as assessed by doubling of spleen volume (by MRI/CT); in addition to an absolute spleen volume of greater than 450 cm³.
- Circulating peripheral blast counts > 10% (requires confirmation after 8 weeks)
- Leukemic transformation defined by an increase in peripheral blood blast percentage to $\geq 20\%$ that is sustained for at least 8 weeks or a bone marrow blast count of $\geq 20\%$
- Hb < 10g/dl with an absolute decrease of at least 3 g/dl from baseline levels (requires confirmation following 2 week of dose interruption/reductions to ensure this is not drug induced cytopenia. In case of Hb stabilizing following dose modification within the 2 weeks, study drug can be re-escalated based on investigators discretion. See section 6.3 for guidance on dosing modifications)
- WBC counts > 25 x 10³/ μ L

- Confirmed MF-7 score of ≥ 30 in addition to an individual symptom score of ≥ 7 in at least one non-splenomegaly related symptom, i.e., tiredness, night sweats, itching (pruritus), bone pain (diffuse not joint pain or arthritis). (Confirmed on two consecutive weeks)
- Death from any cause

As the proposed study intends to investigate the benefit of ruxolitinib in delaying the emergence of MF associated symptoms, MF-7 is expected to objectively evaluate disease progression based on the worsening of symptoms through symptom scores. A clinically relevant threshold of ≥ 30 was set to capture the time point when the patient begins experiencing more symptomatic disease (disease progression) reflected by a minimum of doubling in the baseline MF-7 scores. Additionally, progression by symptom will also require an individual score of ≥ 7 in at least one non-splenomegaly related symptom, i.e., tiredness, night sweats, itching (pruritus), bone pain (diffuse not joint pain or arthritis).

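### The PFS-1 assessment rule names spleen palpation although splenic progression is read by MRI/CT: taken literally it overlooks missed scans, and read with MRI/CT it leaves no adequate scheduled on-treatment visit strictly between Weeks 24 and 48

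*Protocol*

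**What the plan says.** Protocol 10.4.3 fixes the PFS-1 censoring date at the last adequate assessment. It also censors an event that follows two or more consecutive missing assessments, which it equates with at least 24 weeks. Its definitions are:

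- Assessment: "the term assessment corresponds to either spleen palpation, laboratory assessment of hematology parameters" (haemoglobin, WBC, peripheral blasts) or the MF-7 questionnaire.
- Adequacy: "Adequate assessment requires non-missing assessment for all components of PFS".
- Dating, in the next paragraph, when there is no progression: "the assessment date is calculated as the latest of all measurement dates (e.g. laboratory, MRI" being the examples given.

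The splenic criterion in Protocol 10.4.1 reads "Progressive splenomegaly as assessed by doubling of spleen volume (by MRI/CT", together with an absolute volume above 450 cm³. Palpation is not a PFS-1 criterion.

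Protocol 7.2.1.1 schedules scans at screening, then "every 12 weeks and at the end of treatment". Haematology, MF-7 and palpation follow the clinic visits, which between Weeks 24 and 48 fall at Weeks 32 and 40. Protocol 7.1.4 adds that the "Week 36 visit is required only for MRI/CT of the spleen". SAP Table 5-2 repeats this schedule for MRI/CT, haematology and MF-7.

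**The concern.** The spleen measurement named in the missing-data rule is not the one that defines the event, and the same section then treats MRI as a measurement. The rule therefore has two readings, and neither works as intended.

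- **Palpation as written.** Missed scans are invisible to the rule, although palpation cannot show a doubling of volume.
- **MRI/CT, as 10.4.1 implies.** Scans and clinic visits are out of step between Weeks 24 and 48, so no scheduled visit there carries every component.

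This matters because the rule sets the censoring date in the primary analysis and helps decide whether a late-detected event counts. Time to progressive splenomegaly and time to symptomatic progression take over similar censoring rules (10.5.1).

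**Working it through.** **1. The plan's own figure.** Two missing assessments are said to mean at least 24 weeks. On the scan grid (Weeks 12, 24, 36, 48, …) two intervals are 2 × 12 = 24 weeks, which reproduces it. On the palpation/haematology/MF-7 grid (Weeks 4, 8, 12, 16, 20, 24, 32, 40, 48, 60, …) two intervals starting before Week 48 span only 8 to 20 weeks. The 24-week figure therefore fits the MRI/CT schedule. Protocol 7.1.7.2 points the same way: post-treatment follow-up collects haematology, MRI/CT and MF-7 but not palpation.

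**2. Palpation reading.** Suppose the Week 36 and Week 48 scans are missed and the clinic visits are kept. No assessment is missing. A splenic event at Week 60 follows a last scan at Week 24, a gap of 60 − 24 = 36 weeks, and is counted.

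**3. MRI/CT reading.** Components scheduled (Protocol Table 7-1; SAP Table 5-2):

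| Week | Haematology | MF-7 | MRI/CT | All present |
|---|---|---|---|---|
| 24 | yes | yes | yes | yes |
| 32 | yes | yes | no | no |
| 36 | no | no | yes | no |
| 40 | yes | yes | no | no |
| 48 | yes | yes | yes | yes |

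Bone marrow is not treated as a per-visit component, since leukaemic transformation can also be met on peripheral blasts. Adequate visits are Weeks 12, 24, 48, 60, 72, …, with gaps of 12, 24, 12 and 12 weeks. Weeks 4, 8, 16 and 20 also lack a scan, but the gap there stays at 12 weeks. An event-free patient cut off just before Week 48 is censored nearly 24 weeks back, despite a scan at Week 36 and laboratory and MF-7 data at Week 40.

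**4. Events that could be lost if an inadequate visit were also counted as missing.** The text does not say this. Time from the last adequate visit to an event seen at Week 40 is 40 − 24 = 16 weeks; at Week 12 or Week 24 it is 12 weeks. None reaches 24. Only Week 48 does: 48 − 24 = 24.

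Inputs (Protocol 10.8): 160 per arm, exponential PFS with medians 50 and 100 months, 15% cumulative dropout at month 48.

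- Event hazards: ln 2/50 = 0.01386 and ln 2/100 = 0.00693 per month. Dropout hazard (taken as exponential): −ln 0.85/48 = 0.00339.
- Expected events between times a and b per arm: 160 × h/(h+d) × [e^(−(h+d)a) − e^(−(h+d)b)].
- Weeks 24–48 (5.52 to 11.04 months): 10.6 placebo + 5.6 ruxolitinib = 16.2, about 18% of 90.
- Weeks 40–48 (9.20 to 11.04 months): placebo 160 × 0.804 × (0.8533 − 0.8266) = 3.4; ruxolitinib 160 × 0.672 × (0.9095 − 0.8924) = 1.8; total 5.3.

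So about 5 of 90, if each event is first seen at the next haematology/MF-7 visit. The documents give no mix of event types. Deaths carry their own dates and would lower the figure. Splenic events accrue from the Week 36 scan to the Week 48 scan, so if every event were splenic the same formula over Weeks 36–48 gives 5.2 + 2.8 = 8.0.

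**The case against.** The two faults belong to alternative readings and do not hold together. If palpation is accepted as the spleen component, Weeks 32 and 40 carry everything required. That is correct, and it is why the second fault is stated only for the MRI/CT reading and only for scheduled on-treatment visits; an end-of-treatment visit in the interval can be complete.

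One evaluation may also be meant to combine measurements from different dates, since 10.4.3 takes the latest of several and refers to an evaluation number. That would repair the interval. But the term is undefined and nothing joins Week 36 to Week 32 or Week 40.

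A reader might infer more: that a fully adherent patient with a laboratory or MF-7 event at Week 40 is censored at Week 24, or that some 17 of 90 events vanish (5.4 + 5.3 at Weeks 40 and 48, plus 3.0 + 2.8 at Weeks 12 and 24). The documents do not support this. Section 10.4.3 uses adequacy to date censoring and missingness to discard events, and does not equate them; a scan never scheduled is not a missed one. The 24-week minimum also rules out Weeks 12, 24 and 40.

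Protocol 10.4.5 already plans a sensitivity analysis that counts progression after two or more missing assessments as an event. This softens any loss of events. It does not make missed scans visible or correct the back-dated censoring of event-free patients.

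**Conclusion.** The rule needs correcting. The wrong modality is plain on the text: 10.4.3 conflicts with 10.4.1, with 7.2.1.1 and with its own next paragraph. What follows depends on the reading.

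- Literal (palpation): splenic events found after a 36-week unscanned gap are kept, contrary to the evident purpose of the 24-week rule.
- MRI/CT: 0 of 3 scheduled visits strictly between Weeks 24 and 48 is adequate, and adherent event-free patients can be censored up to 24 weeks early.
- MRI/CT, with inadequate visits also counted as missing: losses are confined to events first seen at Week 48, at most about 5 of 90 when events surface at haematology/MF-7 visits, with the dependence on event mix shown in the working.

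The 16 or so events expected in Weeks 24–48 show how much of the trial the interval covers; they do not estimate bias. Alpha, power and the 90-event target are untouched. SAP 2.5 states that PFS is not derived after early termination, so this is a defect in the protocol's primary-endpoint rule and does not alter the abbreviated report.

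**What to change.** In Protocol 10.4.3:

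1. Replace spleen palpation with spleen volume by MRI/CT.
2. Judge adequacy and missingness for each component against its own schedule, and define the evaluation that combines them, for example by pooling the Week 36 scan with the adjacent haematology and MF-7 visit. With that pooling, adequate evaluations are 12 weeks apart throughout.
3. State that only a scheduled assessment that was not done counts as missing.

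Apply the same definitions to the sensitivity analyses in 10.4.5 and to the component endpoints in 10.5.1. The cost is wording and derivation logic; no new data or visits are needed. With PFS no longer derived in this trial, the practical use is for the protocol record and for any reuse of this endpoint definition.

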10.4.4 Supportive analyses

A summary of first progression (PFS-1) events will be tabulated by treatment group.

A subgroup analysis of PFS will be performed by IPSS risk group, type & number of HMR mutations, presence of palpable splenomegaly and/or active symptoms as determined by MF-7.

The analysis of PFS will be repeated for per protocol set.

10.4.5 Sensitivity analyses

If progression event occurs between two scheduled assessments then a date of next schedule assessment will be used as end date for PFS and the outcome will be an event.

If a progression event occurs after two or more missing assessments then date of next scheduled assessment will be used as end date for PFS and the outcome will be an event.

If a patient permanent discontinues study treatment for reason other than disease progression and progression event occurs between permanent discontinuation and start of new anti-neoplastic treatment then the actual date of event will be used and PFS will not be censored.

An alternative definition of PFS excluding MF-7 from progression will be performed.

10.5 Secondary objectives

Secondary objectives related to efficacy include overall survival, time to progression, change in spleen length and volume from baseline, change in symptoms using MF-7 from baseline and progression free survival (PFS-2) in the Treatment Period 2.

Another secondary objective is to assess the effect of ruxolitinib versus placebo on patient reported outcomes (PRO), including disease related symptoms, functioning, and health-related quality of life.

Additional objectives include evaluation of the safety profile of ruxolitinib versus placebo.

10.5.1 Secondary efficacy objectives

Time to primary progression (TTP)

TTP is defined as time from randomization until disease progression as defined for PFS-1 excluding death as an event.

The TTP will be analyzed using log rank test on the FAS population according to the treatment group patients were randomized. TTP will be estimated using the Kaplan-Meier method. The median TTP along with 95% confidence intervals (when applicable) will be presented by treatment group.

The Cox regression model will be used to estimate the hazard ratio (HR) of TTP, along with 95% confidence interval.

Time to first progressive splenomegaly (TTPS)

TTPS is defined as time from randomization until earliest time to progressive splenomegaly as assessed by doubling of spleen volume (by MRI/CT); in addition to an absolute spleen volume of greater than 450 cm³. Since this endpoint is a component of PFS the censoring rules are similar to PFS.

TTPS will be analyzed using log rank test on the FAS population according to the treatment group patients were randomized. TTPS will be estimated using the Kaplan-Meier method. The median TTPS along with 95% confidence intervals (when applicable) will be presented by treatment group.

[figure not shown]
A Cox regression model will be used to estimate the HR of TTPS, along with 95% confidence interval.

Time to first symptomatic progression (TTSP)

TTSP is defined as time from randomization until confirmed MF-7 scores of ≥ 30 with at least one symptom score ≥ 7 in at least one non-splenomegaly related symptom, i.e., tiredness, night sweats, bone pain (diffuse not joint pain or arthritis), itching (pruritus) (confirmed on two consecutive weeks). Since this endpoint is a component of PFS the censoring rules are similar to PFS-1.

TTSP will be analyzed using log rank test on the FAS population according to the treatment group patients were randomized. The time to symptomatic progression will be estimated using the Kaplan-Meier method. The median TTSP along with 95% confidence intervals (when applicable) will be presented by treatment group.

A Cox regression model will be used to estimate the hazard ratio (HR) of TTSP, along with 95% confidence interval.

Quality-adjusted life years (QALY)

EQ-5D-5L health states will be converted into index values (utilities) from which the QALY will be calculated.

QALY will be summarized descriptively by treatment arm.

Change in symptoms using MF-7

See [Section 10.5.6](#).

Change in EQ-5D from baseline

See [Section 10.5.6](#).

Overall survival

OS is defined as the time from date of randomization to date of death due to any cause. If a patient is not known to have died, then OS will be censored at the last date the patient was known to be alive.

The analyses for OS will be based on the FAS population according to the randomized treatment group of the patients. OS will be estimated using the Kaplan-Meier method. The median OS along with 95% confidence intervals (when applicable) will be presented by treatment group. A Cox regression model will be used to estimate the HR of OS, along with 95% confidence interval.

Progression free survival after primary progression (PFS-2)

Patients who experienced a first progression (PFS-1) event in either splenomegaly or symptoms (MF-7 score) will be followed for second progression events, defined below. All patients randomized in the study (FAS) will be included in the PFS-2 analysis. PFS-2 is defined as the time from date of randomization until second disease progression or death from any cause, whichever first. Patients alive and for whom a second disease progression has not been observed should be censored at the last time known to be alive and without second disease progression.

Second disease progression is the earliest time for one of the following events:

- Spleen volume increases $\geq 25\%$ over PFS-1 (new baseline) with an absolute volume $> 450 \text{ cm}^3$
- MF-7 score $\geq 25\%$ over PFS-1 (new baseline) with absolute scores ≥ 30 , an individual symptom score of ≥ 7 in at least one non-splenomegaly related symptom, i.e., tiredness, night sweats, itching (pruritus), bone pain (diffuse not joint pain or arthritis) (Confirmed on two consecutive weeks)

The thresholds for evaluation of progression in the ruxolitinib Treatment Period 2 ($\geq 25\%$ over PFS-1 for both spleen volume increases and MF-7 score worsening) were defined to account for any lack of treatment effect in the post progression Treatment Period and prevent premature discontinuation from treatment due to any transient and borderline worsening in the

symptoms (MF-7 score) and spleen sizes in the immediate post progression period while the patient is switching therapy.

In addition, the following post primary progression parameters assessed in Treatment Period 2 will be summarized descriptively.

- Change in MF-7: Number of patients with 50% reduction in MF-7 score from PFS-1 will be tabulated.
- Change in spleen volume and change in palpable spleen length below costal margin: Number of patients with 35% reduction from PFS-1 will be tabulated.

10.5.2 Safety objectives

10.5.2.1 Analysis set and grouping for the analyses

For all safety analyses, the safety set will be used. All listings and tables will be presented by treatment group.

The overall observation period will be divided into three mutually exclusive segments:

1. pre-treatment period: from day of patient's informed consent to the day before first dose of study medication
2. on-treatment period: from day of first dose of study medication to 30 days after last dose of study medication
3. post-treatment period: starting at day 31 after last dose of study medication.

